6.4.3 Investigational product compliance management and record

Each subject will be instructed by the investigator about the importance of being compliant with clinical trial treatment as well as the importance of returning their investigational product (used and/or not used) at day 1 post-treatment.

The investigational product will be collected and counted at day 1 post-treatment by the investigator or designee.

Subjects will also be questioned by the investigator regarding the skin preparation, application technique of investigational product, the daylight exposure conditions and the use of any other additional topical, systemic drug as well as OTC product.

A subject's questionnaire will be given to each subject in order to record the information on treatment procedure. The investigator will review the subject's questionnaire at visit 2.

The return of used/unused investigational product will be appropriately documented on the product dispensation log by the investigator or designee.

6.4.4 Storage of investigational product

The investigator has to agree to keep all investigational products in a safe, temperature controlled and secure area with restricted access, in accordance with applicable regulatory requirements (e.g., in the site pharmacy, if applicable).

Investigational products should be stored at appropriate storage conditions specified by *GALDERMA R&D* (see section [6.1.1](#)).

The investigator will inform each subject about the storage conditions until treatment application.

6.4.5 Return of investigational product

The investigator will inform each subject about the importance of returning their investigational products (used and/or not used) at the visit 2.

In the event of early termination/suspension of the clinical trial for safety reasons, a rapid recall of the trial product(s) will be initiated. The investigator or designee must immediately instruct all subjects to not perform the clinical trial treatment procedure and return the investigational product to the clinical trial site.

As a general procedure, *GALDERMA R&D* will provide the investigator with a detailed list of units being recalled so that any of the units remaining on site can be put immediately into quarantine.

6.5 Blinding

The present study design is considered as an open study and subjects will receive commercially packaged study products.

7 STUDY ASSESSMENTS

Clinical evaluations should be performed by the same investigator throughout the clinical trial.

If it is not possible to use the same investigator to follow a subject, then evaluations should overlap for at least one visit in order to examine the subject together and discuss findings. This should be documented in medical source documents.

7.1 Subject Reported Outcomes (PRO):

The day of treatment after daylight exposure and at Week 12/Early termination, subjects will complete a questionnaire regarding the treatment procedure (skin preparation, study product application, weather condition daylight exposure, skin discomfort, efficacy, overall satisfaction, etc.) (Appendices 1 & 2).

7.2 Efficacy assessments

7.2.1 AK lesion assessment

7.2.1.1 AK lesions mapping and numbering at baseline

At baseline, the investigator will map the targeted anatomical area and mark each AK lesion within the anatomical area using a transparent plastic sheet. The total number of lesions will be reported in the eCRF.

7.2.1.2 Lesion's response at week 12

At last visit the investigator will use the transparent plastic sheet to locate the anatomical area defined at baseline and the treated AK lesions.

For each pre-existing AK treated lesion present at Baseline, the lesion response will be evaluated at week 12 as follow and reported in the eCRF:

Table 3 - Lesion response

Complete response (CR)	1	Complete disappearance of the lesion, visually and by palpation
Non-complete response (NCR)	0	Non-complete disappearance of the lesion

7.2.1.1 New AK lesions numbering at week 12

Any AK lesion in the anatomical area identified at Week 12 but not at Baseline is defined as a new lesion. The total number of new lesions will be recorded in the eCRF but not taken into account in the lesion response assessment.

At the last visit, lesions in non-complete response or newly appeared lesions will be treated at the discretion of the investigator (off study).

7.2.2 Clinical assessment of the subject's skin aspect

At last visit, for each lesion that has responded completely (see [table 3](#)) the investigator will assess the subject's skin aspect on the following signs or symptoms: scarring, atrophy, induration, redness or change in pigmentation. The clinical assessment of skin aspect will be graded for each lesion as follow:

Table 4 – Skin aspect assessment

Excellent	3	No scarring, atrophy or induration, and no or slight occurrence of redness or change in pigmentation compared to adjacent skin
Good	2	No scarring, atrophy or induration but moderate redness or change in pigmentation compared to adjacent skin
Fair	1	Slight to moderate occurrence of scarring, atrophy or induration
Poor	0	Extensive occurrence of scarring, atrophy or induration

7.3 Safety assessments

A safety assessment will be conducted for all subjects at the baseline visit (after the ICF has been signed) and every subsequent visit. The safety parameters which are adverse events and subject's self-assessment of pain should be recorded as described in the section [7.3.1](#) and [7.3.2](#).

7.3.1 Adverse Events

Adverse events (AEs) are to be monitored throughout the course of the clinical trial.

All AEs including local skin reactions are to be reported on an Adverse Event Form of the eCRF with complete information as required. If AEs occur, the main concern will be the safety of the subject. At the time of the ICF signature, each subject must be provided with the name and telephone number of clinical trial center personnel for reporting AEs and medical emergencies.

7.3.2 Subject's self-assessment of pain

After the treatment procedure when 2 hours daylight exposure is completed, the subject will be requested to assess the maximal pain felt during the duration of the light exposure. The pain sensation will be assessed on an 11-point Numeric Rating Scale (NRS), where 0 = no pain at all and 10 = extreme pain and will be reported by the subject in the first subject questionnaire.

Table 5 - NRS - subject's self-assessment of pain

7.4 Other assessments

7.4.1 Photodamage assessment by Dovers Scale

At baseline visit and last visit, the investigator will assess the skin photodamage of the anatomical area using the following scale:

Table 6 - Dover's modified global photodamage score

0	Skin smooth to the touch without significant fine lines, coarse lines, erythema, telangiectasia, sebaceous hyperplasia, or unevenness in pigmentation in any of the scalp/facial areas (cheeks, forehead, and the perioral area)
1	Scalp/facial skin (on the cheeks, forehead, or the perioral area) shows 1 area of significant roughness, coarse lines, erythema, telangiectasia, sebaceous hyperplasia, dyspigmentation (hypopigmentation or hyperpigmentation), or fine lines
2	Scalp/facial skin (on the cheeks, forehead, or the perioral area) shows 2 areas of significant roughness, coarse lines, erythema, telangiectasia, sebaceous hyperplasia, dyspigmentation, or fine lines; or shows roughness, coarse lines, erythema, telangiectasia, sebaceous hyperplasia, dyspigmentation, and fine lines in 1 area
3	Scalp/facial skin (on the cheeks, forehead, or the perioral area) shows 3 areas with significant roughness, coarse lines, erythema, telangiectasia, sebaceous hyperplasia, dyspigmentation, or fine lines; or shows roughness, coarse lines, erythema, telangiectasia, sebaceous hyperplasia, dyspigmentation, and fine lines in 2 areas
4	Scalp/facial skin shows any degrees of photodamage greater than level 3

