- c) Affix the tear-off portion of the label on the product dispensation log and report the required information on the labels if applicable.
- d) Provide appropriate verbal and written instructions on how to properly use the investigational product(s) and how to perform the treatment procedure (see instruction in section 6.1.4)
- e) Emphasize the importance of complying with the given instructions and treatment; instruct the subject to bring back the dispensed investigational product(s) at the next visit.

12. Dispense to the subject any associated non-investigational product(s).

13. Give and provide instruction to the subject how to use the provided Moisturizer in case some tolerability reactions occur (see 0).

14. Remind the Subject to avoid sun exposure of the treated anatomical area and the use of sunscreen for about 2 days following treatment procedures.

15. Assess the skin photodamage of the selected anatomical area using the Dover's modified global photodamage score (see 7.4.1).

16. Provide guidance on the satisfaction questionnaire (see appendix 1) and ask the subject to fill it out the day of treatment after the daylight exposure. Remind the subject to return it at the next study visit (Day 1 post-treatment).

17. *For selected sites only*, take photographs of the target anatomical area according to the provided procedure only if subject has agreed on the approved photo release consent form.

18. For all female subjects of childbearing potential, emphasize the guidelines about contraception and risks in case of pregnancy.

19. Instruct the subject to call you the day of treatment to confirm the treatment has been well completed and to schedule the next study visit (Day 1 post-treatment). **If you have not heard of subject one week after the baseline, contact him/her to get news and refer to section 4.4.**

At a minimum, tasks numbered 9, 10 and 15 have to be performed by a Dermatologist.

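### Does applying an area-counting global photodamage score to one selected area call for a counting rule in Section 7.4.1?

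*Combined protocol and SAP*

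**What the plan says.** Three places in the protocol direct the photodamage rating to the treated site. Section 5.5.1 item 15 reads "Assess the skin photodamage of the selected anatomical area", Section 5.5.3 item 5 repeats this for week 12, and Section 7.4.1 states that "the investigator will assess the skin photodamage of the anatomical area using the following scale". Each subject has one such site: inclusion criterion 2 in Section 4.2.1 gives forehead, cheek or chin as examples on the face, or else the balding scalp, and question 6 of Appendix 1 lets the subject tick only one.

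Table 6 in Section 7.4.1 is headed as a global score, graded 0 to 4:

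- Grade 0 requires no significant sign "in any of the scalp/facial areas (cheeks, forehead, and the perioral area").
- Grade 1 reads "Scalp/facial skin (on the cheeks, forehead, or the perioral area) shows 1 area of significant roughness", or any one of the other listed signs.
- Grade 2 needs two areas with any sign, or the full set of signs, ending "and fine lines in 1 area".
- Grade 3 "shows 3 areas with significant roughness" or another listed sign, or has the full set, ending "and fine lines in 2 areas".
- Grade 4 is open-ended: "Scalp/facial skin shows any degrees of photodamage greater than level 3".

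Section 9.1.1.3 lists the score among the other variables, at baseline and week 12. Section 9.1.3 gives ordinal data a frequency distribution and the usual summary statistics. Section 9.1.4 rules out inferential statistics. Section 10.1 provides for a review of the evaluation scales at site initiation and for a site reference manual intended to standardise assessments.

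**The concern.** A scale that separates its grades by counting areas is applied to one area, and the word is not defined for that use. The table supports two readings. Grade 0 lists regions of the face, so an area looks like a region. Grade 1 names the regions first and then counts an area of roughness, which can equally be a patch of skin. The chin is an allowed treatment site that Table 6 does not name, and the table gives no subdivisions of the scalp.

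If raters at the roughly 8 sites read the word differently, the pooled frequency table and mean would combine scores on two bases. If all of them counted regions, a scale printed as 0 to 4 might never exceed 2, and a reader could take that ceiling for mild photodamage. Skin aspect under Section 7.2.2 is graded only on lesions that cleared completely, so this score is the only investigator grading of the treated area's skin as a whole.

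**Working it through.** The plan gives no expected value, distribution or precision for this score, so there is no figure to reproduce. The check is an enumeration of Table 6.

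**Inputs.** One rated site per subject (Section 4.2.1, Appendix 1 question 6). Seven signs (Table 6): roughness, coarse lines, erythema, telangiectasia, sebaceous hyperplasia, dyspigmentation, fine lines.

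**Rule.** Let K be the number of areas that can be counted, *a* the number with at least one significant sign, and *l* the number with all seven (*l* ≤ *a* ≤ K). The grade is the highest one met:

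- grade 1 if *a* ≥ 1
- grade 2 if *a* ≥ 2 or *l* ≥ 1
- grade 3 if *a* ≥ 3 or *l* ≥ 2
- grade 4 if *a* > 3 or *l* ≥ 3

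The last line assumes that grade 4 means going beyond both grade 3 clauses; the table does not say so.

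| Countable areas K | Reachable grades | Count |
|---|---|---|
| 1 | 0, 1, 2 | 3 of 5 |
| 2 | 0, 1, 2, 3 | 4 of 5 |
| 3 or more | 0, 1, 2, 3, 4 | 5 of 5 |

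**Region reading.** One site is K = 1. No sign gives grade 0, one to six signs give grade 1, and all seven give grade 2. Grade 3 is out of reach. Grade 4 is out of reach on the ordered rule above, but a rater who treats it as an open severity judgement could assign it, which gives 0, 1, 2 and 4 (4 of 5).

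**Patch reading.** K is not limited, so all five grades are reachable. The full-set clauses still apply: one patch with all seven signs is grade 2, and two such patches are grade 3.

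**Size of a disagreement.** A forehead with three separate rough patches scores 1 by region and 3 by patch, a difference of 2 grades. If every subject had that same skin and a share *p* were rated by patch, the group mean would be 1 × (1 − *p*) + 3 × *p* = 1 + 2*p*: that is 1 at *p* = 0, 2 at *p* = 0.5 and 3 at *p* = 1. Both *p* and the uniform skin are assumptions. This shows the range of the effect and does not estimate it.

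**Comparison between visits.** If one rater keeps one reading, unchanged skin goes 1 to 1 by region or 3 to 3 by patch. A mixture of readings therefore shifts the level of the scores but creates no change where there was none. It can alter the size of a real change: three patches falling to one is 1 to 1 by region and 3 to 1 by patch.

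**What the possible changes would do.** Declaring the selected site to be one area puts everything from one to six signs in grade 1, so a fall from six signs to one would not show. Declaring that patches are counted keeps five grades but needs a further rule for separating patches. Recording all seven signs at both visits adds 7 × 2 = 14 entries per subject, or 14 × 50 = 700 for the planned 50 subjects. That would answer the scale's habit of joining signs with *or*, which is a property of the instrument whichever area is rated.

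**The case for a change.** The best case for acting is that a grade definition belongs beside the printed scale, that one or two sentences in Section 7.4.1 would cost almost nothing, and that keeping the same investigator for a subject does nothing to make different investigators count alike. With 5 to 10 subjects per site, a difference in reading between sites would pass straight into the pooled table. The site reference manual and the separate SAP announced in Section 9.1 are not among the documents reviewed, so nobody reading the protocol alone can tell whether a rule exists.

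Much of this stands. The protocol does not define the term, both readings are available from the table, and grade 3 cannot be reached on one site if regions are counted. What does not follow is that the plan must change. No disagreement between raters is shown, only that one is possible. The people rating are dermatologists (Sections 5.5.1 and 5.5.3), the scales are gone through with each site team, and the manual exists to standardise such assessments. A definition would also have to pick a reading, and neither is plainly right. The region reading fits the grade 0 text but leaves a very coarse score, and it fits chin and scalp only loosely. The patch reading uses the whole scale but needs a rule that the table does not supply.

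**Conclusion.** The mismatch between a global, area-counting scale and a single rated site is a genuine looseness of wording, but it calls for no change. On one site the reachable grades are 0 to 2, or 0, 1, 2 and 4, if regions are counted, and 0 to 4 if patches are counted. The same skin could differ by 2 grades in the three-patch example.

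Nothing the trial sets out to conclude rests on this score. It is summarised descriptively at two visits, has no change endpoint, enters no test, and is separate from the satisfaction questionnaires, lesion response, pain and adverse events. The planned frequency distribution will itself show whether grades 3 and 4 were used, so a ceiling at grade 2 would be visible and would not be hidden behind a mean.

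This view assumes that initiation training and the manual give raters a workable common reading, which cannot be confirmed from the protocol. If they do not, the consequence is limited to photodamage tables that should be read with caution across sites.

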7.4.2 Photographs (for selected sites)

At selected sites only, standardized digital photographs of the anatomical area will be taken at baseline and week 12 using a digital camera. Detailed procedures will be provided separately.

Only subjects who have signed a Photography Release Consent Form will be photographed at baseline and last visit.

7.4.3 Investigator questionnaire

The investigator will be asked to fill out a questionnaire (appendix 3) once all subjects from his site have completed the study.

7.5 Appropriateness of measurements

All measurements planned in this study are non-invasive.

PRO will be evaluated using a questionnaire after treatment and at the end of the study. Treatment compliance will be evaluated based on the recording of treatment information on the subject questionnaire. The questionnaire will collect specifically information on the treatment

procedure, the subject's opinion on the treatments and on the associated cosmetics products used in the trial.

Efficacy will be evaluated by assessing the lesion response which is a sensitive endpoint widely used in clinical practice to assess cure of AKs. At the Week 12 visit, the Investigator will identify all AK lesions (new or initial) on the anatomical area and will define, for each lesion pre-existing at Baseline, the lesion response as CR or non-CR (see [7.2.1.2](#)). This will allow determining the number and percentage of cured lesions.

The safety of investigational product will be assessed through the reported AEs. To complete safety assessment, the Subject's pain assessment after treatment and Subject's skin aspect at Week 12 will also be measured.

The same investigator will evaluate the same subject at each visit throughout the clinical trial.

8 ADVERSE EVENT

8.1 Definitions

8.1.1 Adverse Events (AE)

According to ICH E2A, an AE is any untoward medical occurrence in a subject or clinical investigation subject administered a pharmaceutical product and which does not necessarily have a causal relationship with this treatment. An AE can therefore be any unfavorable and unintended sign (including an abnormal laboratory value), symptom, or disease temporally associated with the use of a medicinal (investigational) product, whether or not related to the medicinal (investigational) product.

Thus any new sign, symptom or disease, or clinically significant increase in the intensity of an existing sign, symptom or disease since the first visit (including the disease being treated), should be considered as an adverse event. Lack of efficacy should not be considered as an AE.

Each new episode of a chronic disease (e.g., hay fever, allergy, etc.) from the screening visit should be reported as a new AE.

Notes:

- Any new sign or symptom reported by the subject that appears after accidental or intentional overdose or misuse should also be reported as an AE.
- There should be an attempt to report a diagnosis rather than the signs, symptoms or abnormal laboratory values associated with the report of an AE. However, a diagnosis should be reported only if, in the Investigator's judgment, it is relatively certain. Otherwise, symptoms, signs, or laboratory values should be used to describe the AE.
- Pregnancy should not be considered as an adverse event but must be followed up as described in section [8.3](#)
- For an AE of irritation, the "date of onset" should be the date that the first symptom occurred.

8.1.2 Serious Adverse Events (SAE)

A serious adverse event is any untoward medical occurrence that at any dose:

- results in death,
- is life-threatening,
- requires hospitalization or prolongation of existing hospitalization,
- results in persistent or significant disability/incapacity, or
- is a congenital anomaly/birth defect.

Important medical events that may not result in death, be life-threatening, or require hospitalization may be considered as an SAE when, based upon appropriate medical judgment, they may jeopardize the safety of the subject, and may require medical or surgical intervention to prevent one of the outcomes listed in this definition. Examples of such events are intensive treatment in an emergency room or at home for allergic bronchospasm, blood dyscrasias, or convulsions that do not result in hospitalization.

Note:

- The term “life-threatening” refers to an event in which the subject was at risk of death at the time of the event; it does not refer to an event which hypothetically might have caused death if it was more severe.
- Inpatient hospitalization is considered to have occurred if the subject has had to stay in hospital overnight. The criterion for the prolongation of hospitalization is also defined as an extra night at the hospital. Hospitalization may not constitute sufficient grounds to be considered as an hospitalization if it is solely for the purpose of diagnostic tests, (even if related to an AE), elective hospitalization for an intervention which was already planned before subject enrolment in the clinical trial, admission to a day-care facility, social admission (e.g., if the subject has no place to sleep), or administrative admission (e.g., for a yearly examination).

8.1.3 Unexpected adverse drug reaction

According to ICH E6, an unexpected adverse drug reaction is defined as an adverse reaction, the nature or severity of which is not consistent with the applicable study drug information (in this clinical trial: the summary of product characteristics for an approved product at the time of AE occurrence).

8.1.4 Adverse event reporting period

The clinical trial period during which AEs must be reported is the period from when the subject signs the Informed Consent Form to the end of the subject’s participation.

The sponsor should be informed if the investigator becomes aware of any unusual safety information or any safety information that appears to be drug-related involving a subject who has participated in a clinical trial, even after a subject has completed the clinical trial. The investigator should be diligent in looking for possible latent safety effects that do not appear until a medication has been discontinued.

8.1.5 Severity

Severity is a clinical determination of the intensity of an AE and not of a disease.

The investigator will classify the intensity of AEs using the following definitions as a guideline for all AEs occurring during clinical trials conducted or sponsored by GALDERMA. For this classification, the investigator will take into account the possible range of the intensity of the event and report the grade of intensity which is the most appropriate according his medical judgment.

Mild	Awareness of sign or symptom, but easily tolerated
Moderate	Discomfort, enough to cause interference with usual activity
Severe	Incapacitating with inability to work or perform usual activity

